8.4.3.3 Analysis of Secondary Immunogenicity Objective(s)

8.4.3.3.1 Statistical Hypotheses

No statistical testing will be performed for the comparative secondary immunogenicity objectives.

CBER requirements for the aQIV vaccine group translate into following hypothesis:

$$H_{0k}^{(SC)}: \pi_{ik} - \pi_0 \leq 0 \quad \text{vs.} \quad H_{1k}^{(SC)}: \pi_{ik} - \pi_0 > 0$$

$$H_{0k}^{(SP)}: \tau_{ik} - \tau_0 \leq 0 \quad \text{vs.} \quad H_{1k}^{(SP)}: \tau_{ik} - \tau_0 > 0,$$

assuming that responses Y_{ij} , Z_{ij} are independent identically distributed Bernoulli variables $B(1, \pi_{ik})$ and $B(1, \tau_{ik})$, where i denotes vaccine group; $j=1, \dots, n_i$ denotes subject, k denotes strain, π_{ik} and τ_{ik} represent the population proportions of subjects achieving seroconversion and post-vaccination HI titer $\geq 1:40$, respectively, π_0 and τ_0 denote the thresholds for seroconversion ($\pi_0 = 0.3$) and the threshold for proportion of subjects with HI titer $\geq 1:40$ ($\tau_0 = 0.6$).

All hypothesis related to CBER criteria will be tested on unadjusted 5% significance level.

8.4.3.3.2 Analysis Sets

Secondary immunogenicity objectives will be evaluated based on the FAS.

8.4.3.3.3 Statistical Methods

All statistical analyses for HI titers will be performed on the logarithmically (base 10) transformed values. Individual HI titers below detection limit (< 10) will be set to half of that limit (5).

Crude estimates for GMTs, GMRs and pertaining 2-sided 95% CIs will be calculated assuming log-normal distribution of the titers and will be completed by providing minimum, maximum and median titers for each vaccine group.

Binary data (i.e., percentages of subjects with seroconversion and with titer $\geq 1:40$) will be summarized for each group using crude estimates and will be reported together with 2-sided 95% CIs calculated according to Clopper's and Pearson's (1934) method. No multiplicity adjustment to the CI levels will be implemented.

For immunogenicity data, it may be reasonable to consider missing immunogenicity values as missing completely at random (MCAR), i.e., not informative. Therefore, the key secondary analysis will comprise a complete case analysis only, without introducing any bias. Imputation methods will not be used.

8.4.4 Analysis of Exploratory Objectives

8.4.4.1 Analysis of Exploratory Safety Objective(s)

There are no exploratory safety objectives in this study.

8.4.4.2 Analysis of Exploratory Efficacy Objective(s)

There are no exploratory efficacy objectives in this study.

8.4.4.3 Analysis of Exploratory Immunogenicity Objective(s)

Exploratory objectives related to the MN-assay will be evaluated using methods for lognormal and binomial data as described in the [Section 8.4.3.3.3](#).

Evaluation of a Serological Predictor of Protection Against Influenza

The immunogenicity data of the blood draw 21 days after vaccination from all subjects reporting an influenza case and subjects randomized from the population without an influenza case serving as the control group will be used to evaluate the relationship between antibody levels tested with the HI assay and clinical protection from influenza.

The Prentice criterion will be used to assess, whether an immunologic correlate of protection can be determined.

To accommodate the criterion a linear logistic regression model will be fitted with vaccine group included as independent predictor and incidence of influenza as dependent variable to show that the observed vaccine effect be explained in a statistical model using immunologic data.

A second logistic regression model will be fitted, adjusted for log-transformed antibody titer and vaccine group to determine the effect of antibody titer on the incidence of influenza. Then, the relationship between the occurrence of influenza and antibody titer level will be modeled using the logistic regression model advocated by Dunning that accommodates both antibody titers and factors independent of antibody titers.

In this model, the probability that a subject develops influenza is the probability that the subject is susceptible multiplied by the probability that susceptible individuals develop disease. Susceptibility is characterized by the probability l , and the probability that a subject with titer t is protected is represented by a 2-parameter logit function. Analyses will be conducted to determine the level of HI (or other assays that might be performed) antibody titer associated with 50%, 60%, 70%, 80% and 90% probability of protection.

The statistical and modelling considerations of estimating correlates of protection will further described in the SAP.

8.5 Sample Size and Power Considerations of Primary and Secondary Objectives

Efficacy objectives:

Sample size and power consideration for the aQIV efficacy objective is based on criteria for demonstrating efficacy in placebo controlled studies provided in CBER guidance, specifically that the study should be powered to assess the lower bound of the two-sided 95% CI of vaccine effectiveness, anticipated to be substantially above zero. This study is planned using a group sequential design. The power of Cox Regression which is planned to be used for analysis is dependent on the overall number of influenza cases, so the sample sizes on number of subjects described in this section is provided more for operational reasons. Additional information on the planning of number of subjects that may need to be enroled if it is decided to continue enrolment after interim analyses is described in [Section 8.6](#).

For the primary efficacy objective: with 1-sided alpha of 2.5% and assuming an attack rate of influenza of 3.5% among subjects enroled in the non-influenza comparator group and 1.4% among the aQIV group, i.e. 60% assumed vaccine efficacy for aQIV, 238 events (i.e. 4,860 subjects per group under the assumed ERs) are needed with 86.5% power to show the absolute efficacy of aQIV versus non-influenza comparator, in preventing first occurrence RT-PCR-confirmed influenza A and/or B, due to any strain of influenza regardless of antigenic match to the strains in aQIV, in subjects ≥ 65 years of age, using a margin of 40% for lower bound of the CI for absolute vaccine efficacy.

For the first secondary efficacy objective: with a group vaccine efficacy of 65% but expecting conservatively reduced event rates of influenza cases due to matched strains of 2.5% among subjects in the non-influenza comparator group and 0.9% among the aQIV group then 144 events has estimated power approximately 88.5% to show the absolute efficacy of aQIV versus non-influenza comparator, using a margin of 40% for lower bound of the CI.

Assuming a drop-out rate of 10%, approximately 10,692 subjects \geq 65 years, 5,346 per vaccine group will be randomized to receive either aQIV or non-influenza comparator (Boostrix®) in a 1:1 allocation ratio, stratifying by age (\geq 65 to 74 and \geq 75 years of age), study site and by low vs high risk of influenza complications (score <50 vs \geq 50).

Immunogenicity objective:

Anti-HA antibody will be measured using a validated haemagglutination inhibition (HI) assay with egg-derived HA antigens from homologous strains of the virus.

The immunogenicity objective is considered as secondary and so no alpha adjustment for multiplicity will be done for the analysis therefore a significance level of 5% (2-sided) or 2.5% (1-sided) was used for sample size calculation. One season in which at least 2800 subjects are anticipated to be enrolled will be selected for the collection of immunogenicity samples. Samples from approximately 2800 subjects participating in the immunogenicity season will be obtained. In order to maintain the study blind blood samples from an equal number of subjects participating in both treatment groups will be collected at Day 1 (baseline) and Day 22 (visit 3).

After all of the specimens have been obtained a subset of samples from those collected will be randomly selected on a 4:1 ratio for analysis. In total approximately 1,702 samples are planned to be included the analysis (1,362 aQIV; 340 Boostrix). The details and the guidelines regarding the selection process of these samples can be found in the SAP.

Following assumptions from the V70_27 study in elderly adult subjects were used: specifically after aTIV vaccination, seroconversion rates, H1N1: 77%, H3N2: 74% and B: 47%, and percentages of subjects with a HI titer \geq 40, H1N1: 91%, H3N2: 99%, B: 64%.

With samples from at least 1,362 enroled subjects (1,226 evaluable subjects assuming a rate of 10% for missing data in the aQIV group) there will be enough power to evaluate achievement of CBER criteria with all four strains contained in the vaccine (see [Table 8.5-1](#)).

Table 8.5-1: Power to assess CBER criteria for subjects ≥ 65 years of age

Strain	π_i (proportion in aQIV, based on data of V70_27)	π_0 (CBER threshold)	Sample size for aQIV	Marginal Power
Proportion of subjects with Seroconversion				
H1N1	77%	30%	1226	99%
H3N2	74%	30%	1226	99%
B strains	47%	30%	1226	99%
Proportion of subjects with HI titer $\geq 1:40$				
H1N1	91%	60%	1226	99%
H3N2	99%	60%	1226	99%
B strains	64%	60%	1226	82%

Safety objectives:

With 4,860 evaluable subjects in each treatment group, the probability of detecting a rare safety event which occurs at 0.001 (1/1000) rate will be 99%. With 1,000 evaluable subjects in each treatment group of the Solicited Safety Set, the probability of detecting an event which occurs at a rate of 0.002 will be $\geq 86\%$, assuming a drop-out/missing data rate of up to 5%.

Sample size calculations were performed using nQuery 7.0 and SAS 9.2.

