Name of Sponsor: Seqirus UK Ltd.	Protocol number: V118_18	Generic name of study vaccine(s): MF59-adjuvanted Quadrivalent Subunit Inactivated Egg-derived Influenza Vaccine Tetanus Toxoid, Reduced Diphtheria Toxoid and Acellular Pertussis Vaccine, Adsorbed
microneutralization).		

Name of Sponsor: Seqirus UK Ltd.	Protocol number: V118_18	Generic name of study vaccine(s): MF59-adjuvanted Quadrivalent Subunit Inactivated Egg-derived Influenza Vaccine Tetanus Toxoid, Reduced Diphtheria Toxoid and Acellular Pertussis Vaccine, Adsorbed
Number of Subjects Planned:		
As described in the study design section this study will employ group sequential design and therefore the total study size (and study duration) will depend on the number of RT-PCR confirmed influenza cases observed during the influenza seasons (see Section 3.7, DMC and Section 8.6, Interim Analysis).		
The sample size, among other factors, depends mainly on the number of PCR-confirmed influenza cases observed during the influenza seasons so the overall number of subjects to be recruited may change and enrolment over multiple seasons may be required to ensure 238 PCR-confirmed influenza cases have occurred and/or based on the results of the interim analysis for efficacy and futility. It is anticipated that in order to obtain 238 cases, including a drop-out rate of 10%, approximately 10,692 subjects \geq 65 years, will need to be enrolled into the trial. Approximately 5,346 subjects will be enrolled per vaccine group will be randomized to receive either aQIV or non-influenza comparator (Boostrix [®]) in a 1:1 allocation ratio, stratifying by age (\geq 65 to 74 and \geq 75) and by comorbidity status (at risk/not at risk, see Section 5.1.2, Screening).		
Specimens from those collected during the immunogenicity season will be randomly selected in a 4:1 ratio for analysis. In total approximately 1,702 of the up to 2800 samples collected are planned to be included the analysis (1,362 aQIV; 340 Boostrix). The serum samples may also be analyzed to facilitate the estimation of immune correlate of protection.		

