where HR is defined as hazard ratio of the incidence of protocol defined ILI in aQIV versus a non-influenza comparator that will be estimated by the proportional hazards model. More details on the analysis methods will be described in the Statistical Analysis Plan (SAP).		
The study is successful if the lower-limit (LL) of the two-sided 95% confidence interval (CI) (to be adjusted for one interim analysis) of absolute vaccine efficacy endpoint > 0.4 . In case another interim analysis is necessary the type 1 error alpha and hence the CI will be adjusted.		
Overall Study Success Criteria:		
The study is successful if the primary efficacy objective is achieved.		
Sample Size and Power Calculation for Primary Objective:		
Sample size and power consideration for the aQIV efficacy objective is based on criteria for demonstrating efficacy in placebo controlled studies provided in CBER guidance, specifically that the study should be powered to assess the lower bound of the two-sided 95% CI of vaccine effectiveness, anticipated to be substantially above zero.		
This study is planned using a group sequential design. The power of Cox Regression which is planned to be used for analysis is dependent on the overall number of RT-PCR		

Name of Sponsor: Seqirus UK Ltd.	Protocol number: V118_18	Generic name of study vaccine(s): MF59-adjuvanted Quadrivalent Subunit Inactivated Egg-derived Influenza Vaccine Tetanus Toxoid, Reduced Diphtheria Toxoid and Acellular Pertussis Vaccine, Adsorbed
confirmed influenza cases, so the sample sizes on number of subjects described in the sections above is provided more for operational reasons. Additional information is described in Section 8.6, Interim Analysis .		
For the primary efficacy objective: with 1-sided alpha of 2.5% (adjusted for possible interim analysis) and assuming an attack rate of influenza of 3.5% among subjects enroled in the non-influenza comparator group and 1.4% among the aQIV group, i.e. 60% assumed vaccine efficacy for aQIV, 238 events (i.e. 5,346 subjects per group under the assumed event rates (ER)) are needed with 86.5% power to show the absolute efficacy of aQIV versus non-influenza comparator, in preventing first occurrence RT-PCR confirmed influenza A and/or B, due to any strain of influenza regardless of antigenic match to the strains in aQIV, in subjects \geq 65 years of age, using a margin of 40% for lower bound of the CI for absolute vaccine efficacy ² .		

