For the first secondary efficacy objective: With group vaccine efficacy of 65% but expecting conservatively reduced ERs of RT-PCR confirmed influenza cases due to matched strains of 2.5% among subjects in the non-influenza comparator group and 0.9% among the aQIV group then 144 events are estimated with power approximately 88.5% to show the absolute efficacy of aQIV versus non-influenza comparator, using a margin of 40% for lower bound of the 95% CI.		
Assuming a drop-out rate of 10%, approximately 10,692 subjects \geq 65 years, 5,346 per vaccine group will be randomized to receive either aQIV or non-influenza comparator (Boostrix®) in a 1:1 allocation ratio, stratifying by age groups: \geq 65 to 74 and \geq 75 years of age and by the presence or absence of medical co-morbidity (see Section 5.1.2, Screening for assessment of comorbidity and risk of complications)		

² The attack rate of 3.5% is estimated based on the attack rate published in placebo controlled studies (DeVilliers, 2009; Treanor, 2011; Frey, 2009)

Name of Sponsor: Seqirus UK Ltd.	Protocol number: V118_18	Generic name of study vaccine(s): MF59-adjuvanted Quadrivalent Subunit Inactivated Egg-derived Influenza Vaccine Tetanus Toxoid, Reduced Diphtheria Toxoid and Acellular Pertussis Vaccine, Adsorbed
--	------------------------------------	---

from influenza).

Sample Size for Secondary Immunogenicity Objective (Immunogenicity Subset):

The immunogenicity objective is considered as secondary and so no alpha adjustment for multiplicity will be done for the analysis therefore a significance level of 5% (2-sided) or 2.5% (1-sided) was used for sample size calculation.

Using the following assumptions from the V70_27 study in elderly adult subjects: specifically after aTIV vaccination, seroconversion rates, H1N1: 77%, H3N2: 74% and B: 47%, and percentages of subjects with a HI titer ≥ 40 , H1N1: 91%, H3N2: 99%, B: 64% (Table 1).

With samples analyzed from 1,362 subjects (1,226 evaluable subjects assuming a rate of 10% for missing data) in the aQIV group there will be at least 80% power to evaluate CBER criteria with all four strains contained in aQIV.

Table 1: CBER criteria for subjects ≥ 65 years of age

Strain	π_i (proportion in aQIV, based on data of V70_27)	π_0 (CBER threshold)	Sample size for aQIV	Marginal Power
Proportion of subjects with Seroconversion				
H1N1	77%	30%	1226	99%
H3N2	74%	30%	1226	99%
B strains	47%	30%	1226	99%
Proportion of subjects with HI titer ≥ 40				

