At each interim stage, α -boundaries, forming the adjusted probabilities for the type 1 error, are calculated using error-spending function and if the p-value for the test of primary objective is lower than the respective α -boundary the trial stops for efficacy at this stage. Using the same error-spending-function applied on the overall type 2 error of 0.1 (Power 90%), β -boundaries are calculated, i.e. the adjusted probabilities for the type 2 error β , and if the p-value is higher than the β -boundaries, the trial stops early for futility at this stage.

In other words the trial stops early for efficacy if data collected at this stage allows to demonstrate primary efficacy objective (reject null-hypothesis); and the trial stops early for futility, if the data provides sufficient evidence that the test vaccine is not good as expected (the alternative hypotheses of absolute vaccine efficacy over the protocol-specified margin is not true, i.e $VE < 0.4$). Otherwise, the trial continues to the next stage and more subjects will be enrolled.

The cumulative O'Brien-Fleming type error-spending-function (Lan and DeMets, 1983; option ERRFUNCBOF in SAS® PROC SEQDESIGN) will be used for both α - and β -boundaries; the error-spending function is defined as:

$$E(t; \alpha) = \begin{cases} 1 & \text{if } t \geq 1 \\ \frac{1}{\alpha} 2 \left(1 - \Phi\left(\frac{z(1-\alpha/2)}{\sqrt{t}}\right)\right) & \text{if } 0 < t < 1 \\ 0 & \text{otherwise} \end{cases}$$

where α equals α for α spending function and β for beta spending function, and where t is the information fraction.

With a specified type 1 error, α , and information level t at stage k , the cumulative error is $\alpha E(t; \alpha)$ <https://support.sas.com/documentation/onlinedoc/stat/131/seqdesign.pdf>

If the trial proceeds to the final analysis, the boundary for rejection of null hypothesis is identical to the type 1 error (that is as the 0.025 one-sided alpha level) with power specified for the overall design, and the trial stops to either reject or not reject the null hypothesis of the primary objective.

Additional interim analyses may be requested by the DMC, particularly if the first interim analysis is conducted soon after 119 cases of influenza have been reported. In this case, the DMC may request that a second interim analysis be conducted to allow for greater accuracy to determine if the trial should stop or continue.

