5. SAMPLE SIZE AND POWER CONSIDERATIONS

Efficacy objectives:

Sample size and power consideration for the aQIV efficacy objective is based on criteria for demonstrating efficacy in placebo controlled studies provided in CBER guidance, specifically that the study should be powered to assess the lower bound of the two-sided 95% CI of vaccine effectiveness, anticipated to be substantially above zero. This study is planned using a group sequential design. The power of Cox Regression which is planned to be used for analysis is dependent on the overall number of influenza cases, so the sample sizes on number of subjects described in this section is provided more for operational reasons. Additional information on the planning of number of subjects that may need to be enrolled if it is decided to continue enrolment after interim analyses is described in [Section 8.6](#).

For the primary efficacy objective: with 1-sided alpha of 2.5% and assuming an attack rate of influenza of 3.5% among subjects enrolled in the non-influenza comparator group and 1.4% among the aQIV group, i.e. 60% assumed vaccine efficacy for aQIV, 238 events (i.e. 4,860 subjects per group under the assumed ERs) are needed with 86.5% power to show the absolute efficacy of aQIV versus non-influenza comparator, in preventing first occurrence RT-PCR-confirmed influenza A and/or B, due to any strain of influenza regardless of antigenic match to the strains in aQIV, in subjects ≥ 65 years of age, using a margin of 40% for lower bound of the CI for absolute vaccine efficacy.

For the first secondary efficacy objective: with a group vaccine efficacy of 65% but expecting conservatively reduced event rates of influenza cases due to matched strains of 2.5% among subjects in the non-influenza comparator group and 0.9% among the aQIV group then 144 events has estimated power approximately 88.5% to show the absolute efficacy of aQIV versus non-influenza comparator, using a margin of 40% for lower bound of the CI.

Assuming a drop-out rate of 10%, approximately 10,692 subjects ≥ 65 years, 5,346 per vaccine group will be randomized to receive either aQIV or non-influenza comparator (Boostrix®) in a 1:1 allocation ratio, stratifying by age (≥ 65 to 74 and ≥ 75 years of age), study site and by low vs high risk of influenza complications (score < 50 vs ≥ 50).

Immunogenicity objective:

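### The stated power of 86.5% (238 events) and about 88.5% (144 events) fits an equal split of cases between arms; with the split that the assumed efficacy implies, primary power is about 79-82% under the Table 8.6-1 boundaries or 81-86% at one look, and key-secondary power is about 81-85%

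*Protocol*

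**What the plan says.** For the primary objective, Protocol 8.5 and SAP 5 assume attack rates of 3.5% (comparator) and 1.4% (aQIV), VE 60%, a margin of 40%, one-sided alpha 2.5% and 1:1 allocation. They conclude that "238 events (i.e. 4,860 subjects per group under the assumed ERs) are needed with 86.5% power to show the absolute efficacy". The Synopsis pairs the same power with a different group size: "238 events (i.e. 5,346 subjects per group under the assumed event rates (ER)) are needed with 86.5% power". Elsewhere the Synopsis treats the larger number as already inflated: "It is anticipated that in order to obtain 238 cases, including a drop-out rate of 10%, approximately 10,692 subjects".

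For the key secondary, the stated VE is 65%, the printed rates are "2.5% among subjects in the non-influenza comparator group and 0.9% among the aQIV group", and SAP 5 says "then 144 events has estimated power approximately 88.5% to show the absolute efficacy of aQIV versus non-influenza comparator". The Synopsis words it as "then 144 events are estimated with power approximately 88.5% to show the absolute efficacy".

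On the final test, the text of Protocol 8.6 says "If the trial proceeds to the final analysis, the boundary for rejection of null hypothesis is identical to the type 1 error", that is, 0.025 one-sided. Table 8.6-1, labelled an example, gives 0.00625 (efficacy) and 0.35022 (futility) at 119 events and 0.02275 at 238. Under SAP 12.1 the decision rests on a Wald interval for the log hazard ratio from a Cox model.

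**The concern.** The precision of a log hazard ratio depends on how the cases divide between the arms, not only on their total. The usual events/4 information assumes an even division. That is reasonable for hazard ratios near 1. Here the null ratio is 0.60 and the alternatives are 0.40 and 0.35, so the aQIV arm contributes far fewer cases and the standard error is larger. Power stated on an even split is then too favourable.

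At stake is the planned risk that this efficacy trial misses a true 60% VE, which the plan puts at 13.5%. There is also a question of which event count the key-secondary power belongs to.

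**Working it through.** **Inputs.** From Protocol 8.5: null HR 0.60; HR 0.40 with D = 238; HR 0.35 with D = 144; 1:1 allocation. From Table 8.6-1: p-value boundaries 0.00625, 0.35022 and 0.02275, which are z = 2.498, 0.385 and 2.000.

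**Formulas.** Drift θ = |ln(HR/0.60)| / SE. One-look power is Φ(θ − 1.960). The two-stage power uses a bivariate normal with drift θ√0.5 at half information and the three z-values above, with futility applied.

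**Step 1: reproduce the stated figures (equal split, SE = √(4/D)).**
- Primary: ln(0.40/0.60) = −0.4055; SE = √(4/238) = 0.1296; θ = 3.128. One look 87.85%; Table 8.6-1 **86.45%**.
- Key secondary: ln(0.35/0.60) = −0.5390; SE = √(4/144) = 0.1667; θ = 3.234. One look 89.87%; with the same boundaries **88.58%**.

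These match 86.5% and 88.5%. The Freedman form with one look also comes close (87.0% and 88.5%), so the source remains an inference.

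**Step 2: the implied split.** The aQIV share of cases is p = HR/(1 + HR).
- Primary: 0.40/1.40 = 0.286, so 68 aQIV and 170 comparator cases.
- Key secondary: 0.35/1.35 = 0.259, so about 37 and 107.

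**Step 3: power with that split, SE = √(1/[D·p·(1 − p)]).**
- Primary: SE = 0.1435; θ = 2.826. One look 80.7%; Table 8.6-1 79.0%.
- Key secondary: SE = 0.1902; θ = 2.834. One look 80.9%.

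**Step 4: check by less approximate methods.** The Cox simulations for the primary are event-driven, with 4,860 per group.

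| Case | One look at 0.025 | Table 8.6-1 with futility |
|---|---|---|
| Primary, formula | 80.7% | 79.0% |
| Primary, exact binomial enumeration of the Wald test | 82.5% | 81.9% |
| Primary, Cox simulation, HR 0.40 | 84.0% | 80.3-80.6% |
| Primary, Cox simulation, rates read as risks | 85.8% | 82.4% |
| Key secondary, 144 events, formula | 80.9% | not specified |
| Key secondary, 144 events, enumeration | 83.7% | not specified |
| Key secondary, 144 events, Cox simulation | 82.7-82.9% | not specified |

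Reading the rates as risks gives HR = ln(0.986)/ln(0.965) = 0.396. The same reading for the key secondary (HR 0.347) gave 85.0%, in a fixed-follow-up run with 144 expected cases.

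**Step 5: event counts.**
- Primary: 4,860 × (0.035 + 0.014) = 238.1, but 5,346 × 0.049 = 262.0. Also 4,860 × 1.10 = 5,346.
- Key secondary: 4,860 × (0.025 + 0.00875) = 164.0; with the printed 0.9%, 4,860 × 0.034 = 165.2. Neither is 144.
- At 164 cases and HR 0.35, one look: formula 85.7%, Cox simulation about 88.6%, enumeration 89.2%.

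**The case against.** Several replies have force.

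- **Events/4 is a standard approximation.** True, and the stated values follow from it, so this is a choice of method and not a slip in arithmetic. It still does not describe the design at these hazard ratios. Using the null split (0.375) instead gives 85.7% at one look and 84.2% under Table 8.6-1 for the primary, still below 86.5%.
- **The split formula is pessimistic.** This stands. At one look it gives 80.7% where Cox simulation gives 84.0%, or 85.8% with the rates read as risks. A reader might infer that the primary falls well short by every route. The documents do not support that, because the most favourable one-look reading is within a point of the stated figure.
- **Table 8.6-1 is only an example.** This stands: the actual boundaries depend on the case count at the interim. Both sets of results are therefore given.
- **The table does not govern the key secondary.** This stands. That objective is tested only after primary success (Protocol 8.4.3.2.3), and no look or futility rule is set in matched cases. Applying the table to it would give 79.2%, but for a design the plan does not contain.
- **The printed 0.9% is rounding.** Taken literally, 0.9/2.5 is VE 64%, and a reader might infer a contradiction with 65%. But 2.5% × 0.35 = 0.875%, which prints as 0.9% to one decimal, so a more exact figure is all that is needed.
- **More than 144 matched cases are expected.** Correct, but the text attaches 88.5% to 144.

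**Conclusion.** The stated powers are more favourable than the planned design delivers at the stated event counts.

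- **Primary, 238 events:** about 79-82% under Table 8.6-1 with futility and about 81-86% with one look at 0.025, against 86.5%. The chance of missing a true 60% VE is therefore about 18-21% or 14-19%, against 13.5%.
- **Key secondary, 144 events:** about 81-85% at one look, against about 88.5%. At about 164 cases it is about 86-89%. The 88.5% fits that yield better than 144, though this does not show how it was obtained.

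Two inconsistencies stand whatever the method: 144 against a yield of about 164, and the Synopsis linking 238 events to 5,346 per group.

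These figures assume proportional hazards, 1:1 allocation and no covariate adjustment. The SAP's random effects for strata were not modelled.

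A reader might also infer that the event target is wrong or the test invalid. Neither follows: the hypothesis, margin, type I error and target of 238 do not depend on the power statement, and 4,860 evaluable per group does yield 238 cases.

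**What to change.** In the Synopsis, Protocol 8.5 and SAP 5:

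1. Recompute both powers, preferably by event-driven Cox simulation, or by a formula that uses the implied case split. Use the interim and final boundaries that will actually apply.
2. Name the method and the boundaries, and restate the power obtained. Leave the event target unchanged.
3. Say whether 144 is a required count or an expected yield, and reconcile it with about 164.
4. Print the aQIV matched-strain rate as 0.875% if VE 65% is meant.
5. In the Synopsis power sentence, give 4,860 evaluable subjects per group as the number that yields 238 events, and 5,346 as the number after adding drop-out.

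The cost is one rerun of the power program and wording in three places. No event or subject numbers change, but the printed power will be less favourable.
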